12.2. Appendix: COVID-19 Symptom Diary

Information about COVID-19-associated symptoms (listed below [[FDA 2020b](#)]) will be collected in a daily COVID-19 Symptom Diary as described in protocol Section [6.3.1.1](#).

Assessment of Common COVID-19-Related Symptoms and Global Impression Items: Items and Response Options and Scoring

“What was the severity of your [insert symptom] at its worst over the last 24 hours?”	Response Options and Scoring
1) Fever (feeling hot or feverish)	
2) Chills (shivering)	
3) Cough	
4) Sore throat	
5) Congestion (stuffy or runny nose)	
6) Shortness of breath or difficulty breathing at rest	None Mild Moderate Severe
7) Shortness of breath or difficulty breathing with exertion worse than usual prior to diagnosis of COVID-19	
8) Muscle or body aches	
9) Fatigue (low energy or tiredness)	
10) Headache	
11) Nausea (feeling like you want to throw up)	
12) Rate your sense of taste in the last 24 hours	My sense of taste is THE SAME AS usual My sense of taste is LESS THAN usual I have NO sense of taste
13) Rate your sense of smell in the last 24 hours	My sense of smell is THE SAME AS usual My sense of smell is LESS THAN usual I have NO sense of smell
14) How many times did you vomit (throw up) in the last 24 hours?	I did not vomit at all 1–2 times 3–4 times 5 or more times
15) How many times did you have diarrhea (loose or watery stools) in the last 24 hours?	I did not have diarrhea at all 1–2 times 3–4 times 5 or more times
16) In the past 24 hours, have you returned to your usual health (before your COVID-19 illness)?	Yes or No
17) In the past 24 hours, have you returned to your usual activities (before your COVID-19 illness)?	Yes or No
18) In the past 24 hours, what was the severity of your overall COVID-19-related symptoms at their worst?	None, Mild, Moderate, or Severe

12.3. Appendix: Injection Site Reaction Diary

At the Day 1 study visit, participants will be given a ruler and instructed on use of the ruler and the Injection Site Reaction Diary along with an emergency 24-hour telephone number, if needed.

Participants will be instructed to record the worst severity experienced during each recording period (prior 24 hours) of the following local (solicited) AEs through Study Day 4, and, if applicable, whether medication was taken to relieve the symptoms:

- Injection site pain or tenderness
- Erythema/redness at the site of injection
- Induration/swelling at the site of injection

Severity will be assessed for solicited AEs (injection site reactions) by the participant (or, if applicable, with help from their caregiver, surrogate, or guardian/LAR) according to the FDA Guidance for Industry: Toxicity Grading Scale for Healthy Adult and Adolescent Volunteers Enrolled in Preventive Vaccine Clinical Trials ([FDA 2007b](#)).

Because solicited AEs are expected to occur after injections, they will not be assessed for relationship to study drug. Investigators or medically qualified designees will follow all ISRs that are ongoing beyond Day 4 to resolution.

Local Reaction to Injectable Product	Grade 1 Mild	Grade 2 Moderate	Grade 3 Severe	Grade 4 Potentially Life-Threatening ^a
Pain	Does not interfere with activity	Repeated use of non-narcotic pain reliever >24 hours or interferes with activity	Any use of narcotic pain reliever or prevents daily activity	ER visit or hospitalization
Tenderness	Mild discomfort to touch	Discomfort with movement	Significant discomfort at rest	ER visit or hospitalization
Erythema/redness	2.5–5 cm	5.1–10 cm	>10 cm	Necrosis or exfoliative dermatitis
Induration/ Swelling ^b	2.5–5 cm and does not interfere with activity	5.1–10 cm or interferes with activity	>10 cm or prevents daily activity	Necrosis

ER=emergency room.

Note: In addition to grading the measured local reaction at the greatest single diameter, the measurement should be recorded as a continuous variable.

^a Pain/tenderness are not expected to be life-threatening but can still meet Grade 4 criteria based on ER visit or hospitalization.

^b Induration/swelling should be evaluated and graded using the functional scale as well as the actual measurement.

12.4. Appendix: Clinical Laboratory Tests

Hematology (CBC with differential):	Chemistry Panel (Serum):
Hemoglobin	Glucose, non-fasting
Hematocrit	Calcium
Erythrocyte count	Albumin
Mean cell volume	Total protein
Mean cell hemoglobin	Sodium
Mean cell hemoglobin concentration	Potassium
Leukocyte (white blood cell) count	Bicarbonate
Neutrophils	Chloride
Lymphocytes	Urea nitrogen
Monocytes	Creatinine (and calculated eGFR)
Eosinophils	Alkaline phosphatase (ALP)
Basophils	Alanine aminotransferase (ALT)
Platelets	Aspartate aminotransferase (AST)
	Total bilirubin
	Human chorionic gonadotropin (hCG) for females
Coagulation Tests	ADG20 Pharmacokinetics and Immunology
Prothrombin time (PT)/International Normalized Ratio (INR)	ADG20 Serum PK
Partial thromboplastin (PTT)	Anti-Drug Antibodies (ADA, immunogenicity)
SARS-CoV-2 and COVID-19-Related Tests	
SARS-CoV-2 RT-qPCR	
SARS-CoV-2 Genomic sequencing	
SARS-CoV-2 Antibodies	
Respiratory Pathogen Panel (co-infections)	

12.5. Appendix: Country-Specific Requirements

12.5.1. Germany-Specific Requirements

No adolescents, pregnant women, or breastfeeding women will be enrolled in Germany. All content in the protocol specific to enrollment of adolescents or pregnant/breastfeeding women is not applicable to sites in Germany. Specific changes related to the exclusion of adolescents and pregnant/breastfeeding women from the study in Germany and other changes to the protocol specific to clinical sites enrolling participants in Germany are outlined in the sections below.

Throughout the protocol:

To be eligible to participate in the study in Germany, a participant must be capable of signing the informed consent. All references to a participant's legally authorized representative (LAR) in the protocol are not applicable for participants in Germany.

Section 4.1.1 Inclusion Criterion

Inclusion Criterion 1:

Is an adult aged 18 years and above.

Inclusion Criterion 2:

Has had SARS-CoV-2 positive RT-PCR test obtained within 5 days prior to randomization.

Note: In the event the National Testing Strategy is updated to include additional testing methods, those methods will also be allowed for use in this study without a protocol amendment. A historical record of a positive result from a test conducted within 5 days prior to randomization is acceptable. SARS-CoV-2 antibody testing cannot be used for study eligibility.

Inclusion Criterion 5b xii:

Does not apply to participants enrolled in Germany.

Inclusion Criterion 5c:

Does not apply to participants enrolled in Germany.

Inclusion Criterion 9:

Is able to understand and comply with study requirements/procedures based on the assessment of the investigator.

Inclusion Criterion 10:

Is able and willing to provide informed consent.

APPENDIX L. SAFETY MONITORING.....	71
APPENDIX M. SCHEDULE OF EVENTS	72

LIST OF TABLES

Table 1:	Objectives and Endpoints	11
Table 2:	Criteria for Sustained Improvement and Sustained Resolution of COVID-19 Symptoms Through Day 29	18
Table 3:	Programmatic Determination of COVID-19 Severity	28
Table 4:	Additional Secondary Endpoint Analyses	34
Table 5:	Grading of Injection Site Reactions	41
Table 6:	Injection Site Reaction Mapping to MedDRA Coding	42
Table 7:	Study Pausing Guidelines	46
Table 8:	Calculated PK Parameters	50
Table 9:	PK Parameters for Data Selection	50
Table 10:	Analysis Windows	55

LIST OF ABBREVIATIONS

Abbreviation	Definition
ADA	anti-drug antibodies
AE	adverse event
AESI	adverse event of special interest
ANCOVA	analysis of covariance
ATC	anatomical therapeutic chemical
AUC	area under the concentration-time curve
BLQ	below the limit of quantification
BMI	body mass index
CBC	complete blood count
CDC	Centers for Disease Control and Prevention
CI	confidence interval
CONSORT	Consolidated Standards of Reporting Trials
COPD	chronic obstructive pulmonary disease
COVID-19	coronavirus disease 2019
CTMS	PPD Clinical Trial Management System
DAIDS	Division of Allergy and Infectious Diseases
eCRF	electronic case report form
eGFR	estimated glomerular filtration rate
EOS	end of study
EUA	emergency use authorization
FAS	full-analysis set
FDA	US Food and Drug Administration
FSH	follicle stimulating hormone
IA	Interim analysis
ICF	informed consent form
ICH	International Council for Harmonisation
iDMC	Independent Data Monitoring Committee
IM	intramuscular
IRT	interactive response technology
ISR	injection site reaction

Abbreviation	Definition
IV	intravenous
KM	Kaplan-Meier
LAR	legally authorized representative
LLOQ	lower limit of quantitation
MAAE	medically attended adverse event
MAR	missing at random
mAb	monoclonal antibody
MedDRA	Medical Dictionary for Regulatory Activities
mFAS	modified full-analysis set
MI	multiple imputation
MNAR	missing not at random
NIAID	National Institute of Allergy and Infectious Diseases
NP	nasopharyngeal
OTC	over-the-counter
PASC	post-acute sequelae of SARS-CoV-2
PCR	polymerase chain reaction
PCS	potentially clinically significant
PK	pharmacokinetic
PPS	per-protocol set
PT	preferred term
RT-PCR	reverse transcription polymerase chain reaction
RT-qPCR	quantitative reverse transcription polymerase chain reaction
SAE	serious adverse event
SAP	statistical analysis plan
SARS	severe acute respiratory syndrome
SARS-CoV-2	severe acute respiratory syndrome coronavirus 2
SAS	Statistical Analysis System
SD	standard deviation
SOC	system-organ-class
SpO ₂	oxygen saturation
TEAE	treatment-emergent adverse event
TFLs	tables, figures, and listings

Abbreviation	Definition
WGS	whole genome sequencing

1. INTRODUCTION

This SAP describes the planned analyses for ADG20-TRMT-001 (STAMP) based on the clinical study protocol, version 6.0, dated 02-Mar-2022. In addition to the information presented in the statistical analysis section of the protocol (Section 7), which provides the principal features of analyses for the study, this SAP provides statistical analysis details/data derivations. It also documents modifications or additions to the analysis plan that are not principal in nature and result from information that was not available at the time of protocol finalization.

The STAMP study is a randomized, double-blind, placebo-controlled, multi-center adaptive study of the safety, efficacy, PK, and antiviral activity of the mAb ADG20 in the treatment of ambulatory participants with mild or moderate COVID-19 with a high risk of disease progression based on age or co-morbid medical conditions. The study will be conducted in 2 phases with data review conducted by an iDMC throughout.

PPD Biostatistics and programming team, designee of Adagio Therapeutics, Inc., will perform the statistical analysis; SAS Version 9.4 or higher will be used. If the methods in this SAP differ from the methods described in the protocol, the SAP will prevail. Any additional analysis outside of the planned analysis following the Day 29 database soft lock or the final database lock that are not performed by PPD are not included in the SAP.

The STAMP study was impacted by the emergence and global spread of the SARS-CoV-2 B.1.1.529 (Omicron) variant, which was first detected in South Africa and Botswana in November 2021. In vitro assessments of the neutralization activity of ADG20 demonstrated markedly reduced activity against authentic Omicron virus compared with prior variants such that ADG20 is unlikely to demonstrate adequate efficacy against SARS-CoV-2 infections caused by the Omicron variant. As a result, enrollment the study was suspended on 11-Jan-2022 as Omicron had become or was likely to become the predominant variant in regions enrolling the trial.

In response to this global event, the analysis plan for this study was updated to analyze efficacy data collected in participants with a non-Omicron variant of SARS-CoV-2 and safety data collected in all participants. The efficacy in participants with an Omicron variant of SARS-CoV-2 will be exploratory. With this analysis plan, the primary efficacy and safety analyses are planned after a database soft lock. A final safety analysis will occur after all enrolled participants have been followed through 14 months/EOS or have discontinued.

2. OBJECTIVES

The objectives and endpoints are presented in [Table 1](#).

Table 1: Objectives and Endpoints

Objectives	Endpoints
Primary	
To evaluate the efficacy of ADG20 compared to placebo in the treatment of mild or moderate COVID-19 in participants at high risk of disease progression	COVID-19-related hospitalization or all-cause death through Day 29
To evaluate the safety and tolerability of ADG20 compared to placebo through Day 29 in participants with mild or moderate COVID-19 and high risk of disease progression	Assessment of safety through Day 29 based on: 
• The incidence of TEAEs• Incidence of solicited injection site reactions through Day 4• Changes from baseline in clinical laboratory tests (ie, CBC with differential, serum chemistry, coagulation)• Changes from baseline in vital signs (body temperature, heart rate, respiration rate, and systolic and diastolic blood pressure)
Secondary	
To evaluate the effect of ADG20 on the following clinical parameters in participants with mild or moderate COVID-19 and high risk of disease progression 
• Severity of COVID-19• COVID-19-related emergency room visits, COVID-19-related hospitalizations, or all-cause death• Time to sustained resolution of COVID-19 symptoms• COVID-19-related medically attended visits• Time to sustained recovery of COVID-19 symptoms• All-cause mortality	
• Severe/critical COVID-19 or all-cause death through Day 29• COVID-19-related emergency room visits, COVID-19-related hospitalization, or all-cause death through Day 29• Time to sustained resolution of COVID-19 symptoms through Day 29• COVID-19-related medically attended visit (telemedicine, physician office, urgent care center, emergency room, hospitalization) or all-cause death through Day 29• Time to sustained recovery defined as sustained improvement or resolution of COVID-19 symptoms through Day 29• All-cause death through Day 29, Day 60, and Day 90

Objectives	Endpoints
To evaluate the effect of ADG20 on SARS-CoV-2 viral load and clearance in participants with mild or moderate COVID-19 and high risk of disease progression	
Change from baseline in SARS-CoV-2 viral load (\log_{10} copies/mL) to Day 7 (± 1) assessed by RT-qPCR from NP samplesViral load $> 5 \log_{10}$ copies/mL on Day 7 (± 1) based on NP samplesDuration of SARS-CoV-2 viral shedding from Day 1 through Day 29 assessed by RT-qPCR from saliva samplesChange from baseline in SARS-CoV-2 viral load (\log_{10} copies/mL) to Days 3, 5, 7, 11, and 14 assessed by RT-qPCR from saliva samplesSARS-CoV-2 viral clearance (Days 5, 7, 11, 14, 21, and 29) assessed by RT-qPCR from saliva samples (and BLQ/not detected or not detected for NP samples for Day 7)SARS-CoV-2 viral load AUC assessed by RT-qPCR from saliva samples from baseline to Day 29
To evaluate the long-term safety and tolerability of ADG20 compared to placebo in participants with mild or moderate COVID-19 and high risk of disease progression	
Assessment of safety based on:
 
The incidence of TEAEsChanges from baseline in clinical laboratory tests (ie, CBC with differential, serum chemistry, coagulation)Changes from baseline in vital signs (body temperature, heart rate, respiration rate, and systolic and diastolic blood pressure)
To evaluate the PK of ADG20 following IM administration	PK parameters of ADG20: As data permit, C_{max} , T_{max} , AUC_{0-last} , AUC_{0-inf} , CL, Vd, and $T_{1/2}$. Additional PK parameters may be calculated
To evaluate the immunogenicity (ADAs) to ADG20	Incidence of ADAs against ADG20
To evaluate the emergence of resistance to ADG20	Genotypic characterization of viral isolates for reduced susceptibility to ADG20, with phenotypic evaluation as appropriate
Exploratory	
To evaluate the effect of host or viral biomarkers on clinical outcomes	Effect of baseline SARS-CoV-2 specific antibody response on select clinical outcomes
To identify a persistently high viral load threshold for risk of adverse clinical outcomes	
The level of viral load leading to the following adverse clinical outcomes:
 
COVID-19-related hospitalization or all-cause death through Day 29COVID-19-related emergency room visits, COVID-19-related hospitalization, or all-cause death through Day 29Severe/critical COVID-19 or all-cause death through Day 29

Objectives	Endpoints
To evaluate the development of symptomatic COVID-19 or asymptomatic infection in household contacts of study participants after participant receipt of study drug	
Participants with symptomatic COVID-19 among household contactsParticipants with asymptomatic SARS-CoV-2 infection among household contacts
To evaluate the effect of ADG20 on the following parameters 
COVID-19-related mortalityTime to improvement of COVID-19 symptomsPost-acute sequelae of SARS-CoV-2 infection	
COVID-19-related death through Day 29Time to improvement of COVID-19 symptoms through Day 29Incidence of PASC at Day 60, Day 90, and Month 6

ADA=antidrug antibody; AUC =area under the plasma concentration–time curve; AUC_{0-inf}: AUC extrapolated to infinite time; AUC_{0-last}=AUC from zero up to the last concentration \geq lower limit of quantification; CBC=complete blood count; CL=clearance; C_{max}=maximum plasma concentration; IM=intramuscular; NP=nasopharyngeal; PASC=post-acute sequelae of SARS-CoV-2 infection; PK=pharmacokinetic; RT-(q)PCR=(quantitative) reverse transcription-polymerase chain reaction; TEAEs=treatment-emergent adverse events; t_{1/2}=plasma concentration half-life; T_{max}=time to reach C_{max}; Vd=apparent volume of distribution.

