6.3.2.3. Survival Assessment

The participant's survival status (known to be alive or dead) will be determined at the planned time for any missed visit through Month 14 or at any time that the participant is thought to be lost to follow up. In the event that the participant is not able to be reached, site staff should utilize primary and secondary contacts including personal contacts, health care provider, and local hospitals as outlined in the ICF (Section [9.3](#)). As described in Section [6.9.3](#), every effort should be made by site staff to ascertain survival status. If survival status is not known, the date last known to be alive will be recorded.

As required for SAE reporting, a death must be reported in the eCRF within 24 hours of the site becoming aware of the death. As permitted by local guidelines, survival status should be reported for participants who have withdrawn from study participation (including survival status or death available via public records [eg, death certificates or public registers]).

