3.4.1. Clinical Efficacy Assessments

Participants will be asked to complete the COVID-19 Symptom Diary (includes global impression questions) daily from Day 1 to Day 29. The investigator (or designee) will assign an overall COVID-19 severity grade for each visit through Day 29. At scheduled visits on Days 3, 5, 7, 11, 14, 21, 29, 60, 90, and at Months 6, 11, and 14, participants (or guardians/LARs) will be asked to report any medically attended visits. Medically attended visits include telemedicine visits not specified in the protocol, emergency room or urgent care center visits, hospitalization, or visits to a physician's office. COVID-19-related medically attended visits include visits for

attention to worsening signs or symptoms attributed to COVID-19 in the opinion of the investigator. The participant's survival status (known to be dead or alive) should be determined at the planned time for any missed visit through Month 14, or at the time that the participant is thought to be lost to follow-up. At Day 29, participants will be asked about household transmission of SARS-CoV-2 and symptomatic COVID-19.

During the long-term follow-up period (LTFU), participants will be asked questions about their overall health status, including return to usual health and usual activities and any ongoing symptoms associated with COVID-19.

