Fever, chills, sore throat, congestion, shortness of breath/difficulty breathing at rest, shortness of breath/difficulty breathing with exertion, muscle or body aches, nausea, vomiting, diarrhea	Moderate/Severe	Mild/Absent with no worsening (moderate/severe)	Absent
	Mild	Absent	with no recurrence or new symptoms (mild/moderate/severe)
	Absent	with no recurrence or new symptoms (mild/moderate/severe)	
Cough, fatigue, headache	Moderate/Severe	Mild/Absent	Mild/Absent
	Mild	with no worsening (moderate/severe)	with no worsening (moderate/severe)
	Absent		

All-cause mortality through Day 29, Day 60, and Day 90: Defined as death for any reason from Day 1 (postdose) to Day 29, Day 60, and Day 90. In the overall survival analysis, participants who are alive or lost to follow-up at the time of analysis will be censored at the date of last contact.

COVID-19-related mortality through Day 29: Defined as death directly due to COVID-19 or any death for which COVID-19 or COVID-19 complications contributed to the death, as determined by the investigator, a formal autopsy report or death certificate, as recorded on the Death eCRF.

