5.5.4. Additional Secondary Endpoints and Analyses

Analyses of other secondary endpoints in the mFAS-non-Omicron analysis set will be conducted to support the findings of the primary and key secondary efficacy endpoints. The results of these analyses will be considered descriptive in nature and will be analyzed without any procedures to account for multiple comparisons, except as specifically noted. Analysis approaches for the other secondary endpoints (ie, non-key) are summarized in [Table 4](#). In addition to these analyses, listings of viral load based on nasopharyngeal samples; viral load, viral clearance status, viral load AUC, and time to viral clearance based on saliva samples; and medically attended visits will be provided.

Table 4: Additional Secondary Endpoint Analyses

Endpoint	Statistical Analysis Methods
COVID-19-related medically attended visits and all-cause death through Day 29	The methods for the primary efficacy endpoint will be used except without applying multiplicity adjustments (see Section 5.5.1).
Time to sustained recovery in COVID-19 symptoms through Day 29	The methods for the analysis of time to sustained resolution of COVID-19 symptoms through Day 29 will be used (see Section 5.5.3)
All-cause death through Day 29, Day 60, and Day 90	KM methodology will be used to analyze all-cause deaths. The probability of all-cause deaths by each of these time points will be estimated, along with 95% CIs for differences in the probabilities. Survival curves between ADG20 and placebo will be compared using a log-rank test. A Cox Proportional Hazard model will be used to estimate the hazard ratio. The model includes age (continuous), sex (categorical), baseline serostatus (categorical: positive, negative), baseline BMI (continuous), and baseline viral load (continuous as \log_{10} copies/mL) as covariates. Comparison of the survival distributions will use the score test for the hazard ratio from this Cox model.

Endpoint	Statistical Analysis Methods

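### The log-rank test and Cox hazard ratio for all-cause death carry no time limit, so they match none of the endpoint's horizons (Day 29, 60 or 90)

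*SAP*

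**What the plan says.** SAP 2, Table 1, lists the secondary endpoint as "All-cause death through Day 29, Day 60, and Day 90". SAP 3.5.1 fixes the endpoint's horizons: "Defined as death for any reason from Day 1 (postdose) to Day 29, Day 60, and Day 90". For what it calls the overall survival analysis, the same paragraph adds that "participants who are alive or lost to follow-up at the time of analysis will be censored at the date of last contact". No day is given at which follow-up stops.

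SAP 5.5.4, Table 4, lists three kinds of result for this endpoint, and Protocol 7.8, Table 7-2, has the same method:

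- Landmark estimates: "The probability of all-cause deaths by each of these time points will be estimated, along with 95% CIs for differences in the probabilities".
- A whole-curve test: "Survival curves between ADG20 and placebo will be compared using a log-rank test".
- A covariate-adjusted Cox hazard ratio, where "Comparison of the survival distributions will use the score test for the hazard ratio from this Cox model".

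Only the landmark estimates are tied to Day 29, 60 and 90.

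On follow-up, SAP 3.4.1 states: "The participant's survival status (known to be dead or alive) should be determined at the planned time for any missed visit through Month 14". Two locks are planned (SAP 3.2): a soft lock once Day 29 visits are complete, and a Month 14 lock for the final safety analysis. Protocol 5.5 places the efficacy analyses at the soft lock and also foresees an unblinded analysis of data through Month 14. Neither document says which lock supplies the mortality log-rank and Cox results, or the Day 60 and Day 90 results.

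**The concern.** A log-rank test or Cox model uses every event up to each participant's censoring time. With survivors censored at last contact, the p-value, hazard ratio and score test describe mortality over whatever follow-up exists at the data cut. That is not mortality to Day 29, 60 or 90. Other time-to-event endpoints in SAP 3.5 do stop: participants without a symptom event are censored at Day 30 once the Day 29 visit is complete, and viral shedding is censored no later than Day 30. Mortality is left uncapped.

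Two things are at stake. A hazard ratio and nominal p-value for death would be reported under an endpoint name that does not describe them. They could also change between locks although the endpoint has not changed.

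**Working it through.** **1. Is there a figure in the plan to reproduce?** Not for death: the documents give no mortality rate, death count or power for this endpoint. The sizing figures belong to the primary endpoint. For 12% versus 3.6% with 160 per arm, (0.084 − 1.96 × 0.02998) / 0.02961 = 0.852, which gives 80.3% power and agrees with the stated 80% or so. Below I borrow only the 160 per arm (half of about 320) and the 70% reduction. All death rates are my assumptions.

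**2. Which follow-up could enter?** Enrollment stopped on 11 Jan 2022 (SAP 1). The last participants therefore reach

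- Day 29 on 8 Feb 2022 (+28 days),
- Day 60 on 11 Mar 2022 (+59),
- Day 90 on 10 Apr 2022 (+89),
- Day 420, the Month 14 target, on 6 Mar 2023 (+419).

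Protocol Table 6-1 shows that the first 10 participants had been dosed by 7 Oct 2021, which is 124 days before 8 Feb 2022. At the earliest soft lock some follow-up therefore already exceeds Day 90, while the last participants have not reached Day 60.

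**3. Size at the soft lock.** Assumptions: 3% placebo deaths by Day 29, a 70% reduction of these (0.9% on ADG20), 2% per year background mortality in both arms afterwards, and uniform entry over the 100 days from 3 Oct 2021 to 11 Jan 2022. The documents give no first-dose date. Acute cumulative hazards are −ln(0.97) = 0.03046 and −ln(0.991) = 0.00904.

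For a cut on 8 Feb 2022, follow-up is uniform from 28 to 128 days:

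- Mean follow-up beyond Day 90: 38² / 200 = 7.2 days. Expected deaths there: 320 × 0.02 × 7.2 / 365, about 0.1.
- Mean follow-up beyond Day 29, capped at Day 90: 41.8 days, background hazard 0.00229. HR = 0.01133 / 0.03275 = 0.346.
- Uncapped: 49.0 days, background hazard 0.00268. HR = 0.01172 / 0.03314 = 0.354.

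For a cut on 2 Mar 2022 (the date of protocol version 6.0, used only as a later example), the expected late deaths are 320 × 0.02 × 18 / 365, about 0.3, and the HRs are 0.358 capped and 0.377 uncapped.

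**4. Size if the analysis is run at Month 14.** With full follow-up to day T, the ratio of cumulative hazards, which approximates the Cox estimate, is

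HR(T) = [−ln(1 − 0.3p) + r(T − 29)/365] / [−ln(1 − p) + r(T − 29)/365]

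where p is the placebo risk by Day 29 and r is the yearly background rate.

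| p, r | Day 29 | Day 90 | Day 420 |
|---|---|---|---|
| 4%, 1% | 0.30 | 0.32 | 0.44 |
| 3%, 2% | 0.30 | 0.37 | 0.59 |
| 2%, 3% | 0.30 | 0.44 | 0.73 |

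Middle row at Day 90: (0.00904 + 0.00334) / (0.03046 + 0.00334) = 0.37. At Day 420: (0.00904 + 0.02142) / (0.03046 + 0.02142) = 0.59.

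**5. Does the direction depend on the late effect?** Take 10 deaths by Day 90 at HR 0.30 and 5 later deaths, average the log HR over deaths, and use power = Φ(√(d/4) × |ln HR| − 1.96).

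- Capped at Day 90: HR 0.30, power 48%.
- Uncapped, late HR 1.0: HR 0.45, power 34%.
- Uncapped, late HR 0.7: HR 0.40, power 43%.
- Uncapped, late HR 0.30: HR 0.30, power 65%.

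So the hazard ratio moves toward 1 only if the late effect is weaker than the early one.

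**The case against.** The strongest defence is that the endpoint is already analysed at its horizons. The Kaplan-Meier differences with confidence intervals are unchanged by later deaths, and the overall survival analysis can be read as an extra description of the whole curve. The first half stands. The second half is possible, but Table 4 lists the test and hazard ratio under the Day 29/60/90 endpoint and labels nothing as supplementary.

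A reader might infer more than the documents support, in three ways:

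- **That the test is planned to run to Month 14.** No text assigns it to that lock, which the SAP calls a safety analysis. The lock is unspecified, and at the earliest soft lock the effect is negligible (step 3).
- **That later deaths necessarily dilute the treatment effect.** This needs a late hazard ratio nearer 1 than the early one. The documents give no late mortality, and with a half-life of about 97 days (Protocol 1.1) a late effect cannot be excluded. SAP 1 expects inadequate efficacy against Omicron, which makes late protection less likely but does not settle it.
- **That traced deaths count while traced survivors are censored earlier.** The SAP does not define last contact, and nothing excludes survival checks from it. Protocol 6.3.2.3 says "If survival status is not known, the date last known to be alive will be recorded", which concerns people whose status is unknown. This is an ambiguity to close, not a shown bias.

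The objection that separate Cox models at all three days would be unsound also stands. In the 3% case about 160 × (0.03 + 0.009) + 320 × 0.02 × 61/365 = 7.3 deaths occur by Day 90, against six coefficients (treatment and five covariates).

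**Conclusion.** The point holds as a mismatch between endpoint and test. The log-rank test, Cox hazard ratio and score test have no stated horizon and include any death after Day 90 in the database, whichever way those deaths fall. The landmark Kaplan-Meier results are sound.

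Under the assumed rates and entry pattern, the hazard ratio changes by about 0.01 to 0.02 at the soft lock dates examined. It would change from 0.37 to 0.59 (range 0.32–0.44 to 0.44–0.73) only if the analysis were run at Month 14 and late deaths were unrelated to treatment. SAP 5.5.4 treats the endpoint as descriptive and SAP 4.4 leaves it outside the testing hierarchy, so no confirmatory conclusion depends on it. The change is worth making because it is cheap and gives the reported hazard ratio for death a defined meaning at either lock.

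**What to change.** In SAP 3.5.1 and SAP Table 4, with Protocol Table 7-2 aligned:

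- Censor the log-rank and Cox analyses administratively at Day 90, with survivors censored at the earlier of Day 90 and the date last known alive.
- Keep the Kaplan-Meier differences as the Day 29 and Day 60 results, and do not add Cox models at those days. The Day 90 Cox estimate may itself be fragile with so few deaths.
- State which database lock supplies the Day 60 and Day 90 results.
- Show deaths after Day 90 descriptively, in the Kaplan-Meier plot and the death tables.

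This takes a few sentences and one censoring line in the program, and needs no new data. SAP 1 lets the SAP prevail over the protocol. If only the SAP is amended, SAP 7, which reports no changes from the protocol, needs an entry. The edit should be made before unblinding. The cost is fewer deaths in the test: almost none at the soft lock, and about 320 × 0.02 × 330/365 = 5.8 at Month 14 under the middle assumption before drop-out, all outside the stated endpoint.
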